We will exclude individuals with moderate to severe levels of dementia and individuals with active delirium (per neurologist's determination), as these patients are less likely to be referred for neuropsychological evaluation than individuals with mild presentations. We will exclude patients who are legally blind or deaf, due to the auditory and visual components of the study. We will exclude individuals with a brain tumor and individuals who have a confirmed non-AD neurological diagnosis (e.g., Multiple Sclerosis; FTD); moreover, we will exclude individuals who are being evaluated outside of the UCH Memory Disorders Clinic. Finally, we will exclude participants who report active (i.e., within the last 6 months) substance use of illicit drugs such as cocaine or methamphetamines, or who carry a diagnosis of a major psychiatric disorder (e.g., schizophrenia; bipolar disorder).

Additional Consenting Participants:

Participants will be encouraged to bring a care partner, if available, with them to visits (i.e., FF and TeleNP), and the care partner will also provide consent to complete surveys and interviews. Consistent with the target sample for the primary participants, we will recruit up to 80 care partners; however, consistent with standard clinical practice, the availability of a care partner will not be a requirement. There are no age requirements or other inclusion/exclusion criteria for the care partner. We anticipate that most care partners will be co-residing caregivers, although participants may select a close friend as their care partner.

Total potential enrollment number including coverage for screen failures/withdrawals = 300. (Up to 150 patients, plus their care partners if applicable).

Recruitment and Screening:

We will work directly with the Memory Disorders Clinic to recruit participants. In the last two years, the UCH Memory Disorders Clinic served over 5,000 patients.

The referring neurologists (sub-investigators on this study) may directly approach their patients to discuss the proposed study and determine interest in study enrollment. They (i.e., referring neurologist) will provide baseline demographic and diagnostic information (typical vs. atypical AD), patient severity level (MCI vs. Mild Dementia), and their (neurologist) judgment of capacity to consent through a brief REDCap survey to the study psychometrist.

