HIPAA privacy notification language will be incorporated into the informed consent document and will be signed by all participants prior to any procedures being carried out. Informed consent language will include key facts about the study, the study events, timeline, the study participant's role in the study, potential risks and benefits and highlight the fact that participation is completely voluntary and will be signed by all study participants. The informed consent/HIPAA form will specify that the database will receive and store all research data. Information regarding the purpose and procedures for this project will be given in both oral and written form. All study participants will be consented in privacy and will be given as much time as they need to read, discuss and ask questions about study events and their respective roles and participation in the study. They will be reassured that the same ethical and legal codes that govern medical practice

[figure not shown]
also apply to clinical research and they will be given the opportunity to ask questions and receive information regarding the goals and details of this study. If the Principal Investigator or Co-Investigators do not initially participate in the discussion, they will be available to answer questions prior to obtaining written informed consent/authorization.

Subjects may withdraw participation in the study at any time by calling, writing, or emailing the Principal Investigator or study coordinator. Subjects will be unable to withdraw data that has already been analyzed, presented, or published.

B. Study Design and Research Methods

Randomization, Intervention and Neuropsychological Assessment Methods

Study participants will undergo both modalities (FF; TeleNP), conducted 4-6 weeks apart (allowing for maximum of 90 days). Order of modality will be randomized at baseline using a computerized process through REDCap, developed by [name]. Similarly, assignment of supervising neuropsychologist will be randomized and counterbalanced across testing conditions. Our goal of using two neuropsychologists is to minimize bias; specifically, use of the same neuropsychologist for the same patient across both modalities would likely influence their interview approach and diagnostic adjudication due to recollection of the prior assessment.

Abbreviations and Terminology:

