Face-to-face (FF) Assessment (control condition): The participant will undergo an in-person evaluation with the neuropsychologist and psychometrist at the Clinical & Translational Research Center (CTRC) or in Building 400 at CU-AMC. The standard protocol will be administered, including the interview and Core Battery. After completion of the Core Battery and submission of initial ratings, the supervising neuropsychologists may elect to have additional tests administered by the psychometrist as part of a Flexible Assessment. The Flexible Assessment will include a menu of tests that have physical/tactile stimuli (e.g., Design Fluency; Trail Making Test), all of which are excluded from the Core Battery due to lack of adaptability to video-based administration. Upon receipt of the scores from the Flexible Assessment, the neuropsychologist will complete a second form indicating any alterations to their diagnosis based on new information.

TeleNP Assessment (intervention condition): The participant will undergo a video-based TeleNP assessment using a HIPAA-compliant platform (e.g., Zoom). The participant will be at home using a study-provided tablet, and the neuropsychologist and psychometrist will administer the evaluation from either the CTRC or their CU-AMC office. During the scheduled TeleNP assessment, the standard protocol will be administered (i.e., interview and Core Battery). The psychometrist will assist with tablet collection at no direct cost to the participant (i.e., will provide a paid return box; alternatively, participant may drop off tablet if convenient to them)

Data Collection for Clinical Trial Participants:

Medical records:

--Participants will be asked to allow their past, current and future medical record information, to be placed in our RedCap database. The goal is to collect health information pertinent to cognitive functioning in older adults. Because concurrent medical conditions and treatments may impact the participants' health, it is likely that all pertinent past, current and future medical record information will be considered for inclusion in the RedCap database. This will include: symptom history and diagnostic considerations from the participants' neurology notes; laboratory results; health history (i.e., major medical problems); brain imaging results.

Demographics:

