their patients to participate in the study, and they will also document their initial determination of capacity to consent based on clinical assessment. If the patient is interested in participating, the neurologist will provide brief (e.g., contact information; diagnosis; capacity) information to the psychometrist and the psychometrist will set up the initial screening and consent call. All potential participants will be encouraged to include a care partner in the process (i.e., screening/consent, study visits).

All participants will subsequently participate in an informed consent process; if the referring neurologist notes a lack of capacity, the participant will be asked to include their legally authorized representative (LAR) during the screening/consent call. All aspects of the project will be reviewed by the University of Colorado Multiple Institutional Review Board (COMIRB). Before enrollment, study personnel will ensure the subject's full understanding of the research project, including the study objective, risks and benefits, the right to non-participation, review processes, emergency medical treatment, and financial responsibility. Informed consent will provide explicit details regarding confidentiality and sharing of de-identified data with qualified researchers; more specifically, consent forms will indicate that: de-identified data may be shared with qualified investigators outside the University; identifiable information from their in-person assessment will be provided to them and their referring neurologist in a research note. [name], [name], and [name] will also be available to answer questions regarding consent and procedures.

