Strategies to minimize risk: Risks to subjects are minimal and may include loss of confidentiality and psychological discomfort about discussing issues related to their neuropsychological assessment. Prior to enrollment, the study will be explained in a clear and detailed manner by the study coordinator (serving in role as coordinator and psychometrist) and investigators. All participants will be reminded at the beginning of all assessments of their right to terminate the assessment at any time. In the study consent procedure and study activities, we will clearly state that all participants can refuse to answer any questions or to review any of the study materials. Research staff will be trained to address psychological distress and will follow standard procedures for referral for mental health evaluation. We will also reassure patients that if they choose not to be in the study, it will not affect the medical care they normally receive.

We will provide neuropsychological test results from the FF condition (i.e., condition that is most congruent with standard of care) to the referring neurologist and the patient, and this information will also be placed in a research note in their UCH EMR. This will be explicitly noted in consent form and reviewed in detail with the participant. In terms of study results, there is a possibility of practice effects, particularly on memory tests and fluency tests, with serial testing. Studies suggest minimal practice effects in individuals with symptomatic Alzheimer's disease; however, given that we will provide results from the FF assessment to be used in clinical care and potentially for diagnosis, we will mitigate risk in the following way: a) use of alternate forms, where possible and b) require of at least one month between conditions. Based on these strategies, which are also used in standard of care with neuropsychological serial testing, we do not think enrollment in the study poses a significant risk of a clinically meaningful practice effect.

Strategies to manage and protect the privacy of participants and confidentiality of research data: A copy of the consent form will be given to each participant. Maintenance of subject confidentiality is a high priority for the proposed research project. Video-based TeleNP will be conducted using

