HIPAA-compliant platform supported by UC Health and CU Anschutz Medical Campus. Video assessments will not be recorded. All written and audio-recorded data (i.e., stakeholder semi-structured interviews) and consent materials will be given anonymous identification numbers and will be stored on a password protected private database on computers in locked offices. The consent forms and the key for identification of subject names corresponding to identification numbers will be stored in a separate locked file cabinet. For audio-recorded data (i.e., semi-structured interviews), research assistants will redact any spoken identifiers (names, etc.) from transcripts and will label audio-files with a sequential de-identified number. Study data will be collected and managed using REDCap (Research Electronic Data Capture). Only key study personnel will have access to these data. REDCap is a secure web application designed to support data capture for research studies, providing user-friendly web-based case report forms, real-time data entry validation (e.g. for data types and range checks), audit trails, and a de-identified data export mechanism to common statistical packages (SPSS, SAS, Stata, R/S-Plus).

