Diagnosis: While neuropsychologists will be apprised of the study design, they will be blinded to the *specific* referral diagnosis (i.e., typical vs atypical AD); moreover, the neuropsychologist will be asked to provide *their own determination* and given the option of including “Not AD” as their provisional diagnosis. The goal of this approach is to minimize bias and circularity; however, it remains possible that neuropsychologist-specific effects will be present (i.e., tendency to rate participants as “complex”). We will assess in exploratory analyses whether there were provider-specific effects on outcomes. We acknowledge that the division of diagnoses into three categories (i.e., subjective concerns; MCI; dementia) does not fully map onto NIA-AA diagnostic criteria for MCI² and AD dementia¹; however, most neuropsychologists do not have access to fluid/PET biomarkers in clinical practice, thus our approach more pragmatically represents standard of care. Nonetheless, neuropsychologists often do provide specific diagnoses for complex phenotypes, including focal presentations (e.g., posterior cortical atrophy). As an exploratory strategy, we will consider providing an additional diagnostic field for the neuropsychologist to indicate specific considerations in their differential.

Statistical Analysis Framework: We are evaluating equivalence by examining mean Z-scores per cognitive domain, aggregated across multiple tests; however, individual tests have different test-retest reliabilities, which are often evaluated on a patient-specific level through the use of reliable change indices (RCIs). Given the pilot nature of this clinical trial, it is possible that a .5SD difference in mean domain score will not accurately reflect a clinically meaningful difference in individual test scores. As such, we will consider examining test-specific differences across modalities using published test-rest reliability.

Technological Difficulties: We have incorporated several approaches to minimize and troubleshoot technological difficulties, including a pre-visit test call, inclusion of care partner in the process, and provision of a study tablet to all participants. Consistent with Aim 3, **we will track technological issues throughout the study procedures to inform changes that might be beneficial to a larger clinical trial**. In addition, we will include a discussion during monthly team meetings regarding any technological issues that arise.

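### The psychometrist who tests and scores both visits is told the typical/atypical referral label that the neuropsychologists are blinded to

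*Combined protocol and SAP*

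**What the plan says.** Section IV.A, Recruitment and Screening, has the referring neurologist "provide baseline demographic and diagnostic information (typical vs. atypical AD"), together with a severity level and a "judgment of capacity to consent through a brief REDCap survey to the study psychometrist". Informed Consent and Assent, under Adequacy of Protection Against Risks, repeats the flow: "the neurologist will provide brief (e.g., contact information; diagnosis; capacity) information to the psychometrist". Strategies to minimize risk adds that this person is the "study coordinator (serving in role as coordinator and psychometrist"). The wording is singular wherever the psychometrist appears, although no head count is given.

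Under Protocol and Core Battery, the psychometrist gives the battery in both conditions, scores it with an automated norms calculator and passes the adjusted scores to the neuropsychologist, who then records diagnosis and severity.

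Blinding is stated for the neuropsychologists only. Section E, Diagnosis, says: "While neuropsychologists will be apprised of the study design, they will be blinded to the" specific referral diagnosis. The randomization text in Section IV.B says "Our goal of using two neuropsychologists is to minimize bias", because one rater seeing the same patient twice would remember the first assessment. Nothing comparable is said about the psychometrist.

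On records, the Medical records paragraph places "symptom history and diagnostic considerations from the" neurology notes in REDCap. The confidentiality text says "Only key study personnel will have access to these data".

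**The concern.** The blind protects the person who makes the diagnosis but not the person who produces the evidence for it. Much of a neuropsychological score depends on the examiner: prompting, querying, timing, and raw scoring of borderline responses. If the examiner knows that a patient was referred as memory-predominant or as atypical, the scores can drift toward that profile at both visits. Two neuropsychologists working independently from such scores would then agree partly because each set leans toward the same label.

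In an equivalence study this is the unfavourable direction, because a shared influence on both modalities makes them look alike. Aim 2 is most exposed, since its outcome is the diagnosis itself. Aim 1b is stratified by the same label. It is also the circularity that the plan says it wants to limit.

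**Working it through.** The plan gives no figure on this point and no sample-size calculation, so there is no stated result to reproduce. One side check: a 90% interval inside the margins is two one-sided tests at (1 − 0.90)/2 = 0.05, which agrees with the stated alpha.

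**Step 1. Who knows what, and when.**

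| Role | Told the referral label before testing? | Task |
|---|---|---|
| Neurologist | Assigns it | Refers the patient |
| Psychometrist | Yes, stated twice | Tests and scores both visits |
| Neuropsychologist | No, stated as blinded | Diagnoses from interview and scores |

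This is a stated data flow, not an inference from missing detail.

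**Step 2. Aim 1, equal effect at both visits.** If the label shifts a patient's score by b in each modality, the paired difference is (FF + b) − (TeleNP + b) = FF − TeleNP. The shift cancels. With a true difference at the 0.5 margin, the rate of falsely declaring equivalence stays at 5%, for n = 80 or n = 40.

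**Step 3. Aim 1, effects that do not cancel.**
- *Different by modality.* If the label effect differs by c between modalities, the mean difference moves by c. Assume c = 0.1, acting to narrow a true difference of 0.5, and a paired SD between 1.0 and 0.5. False equivalence is then 23% to 55% at n = 80 and 15% to 34% at n = 40.
- *Shrinkage toward an expected profile E.* If each score becomes (1 − k) × score + k × E, the difference becomes (1 − k)(FF − TeleNP), so its mean and SD both shrink by (1 − k). With k = 0.1, SD 1.0 and n = 80, the mean is 0.45 and the SD 0.9. The pass probability is about Φ(0.05 × √80 / 0.9 − 1.664) = Φ(−1.167) = 0.12; simulation gives 0.124. Over SD 1.0 to 0.5, simulation gives 12% to 25% at k = 0.1 and 30% to 72% at k = 0.2.

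The values of c, k and SD are assumptions; the documents supply none of them.

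**Step 4. What the shrinkage rates cannot show.** If the examiner remembers visit 1 and the visit-2 score becomes (1 − w) × visit 2 + w × visit 1, the difference is again multiplied by (1 − w). The algebra is the same, so the rates are the same. They describe any pull that draws the two scores together. They do not say how much comes from the label, which can be withheld, and how much from the examiner's own memory, which cannot.

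**Step 5. Aim 2.** Section F compares the proportion in each diagnostic category between modalities, with a 90% interval required to lie within ±5%. The interval formula is not given. Assume a paired Wald interval and 80 complete pairs. With equal numbers discordant in each direction and D discordant in total, the half-width is 1.645 × √D / 80.
- D = 6: 1.645 × 2.449 / 80 = 0.0504, not equivalent.
- D = 4: 1.645 × 2 / 80 = 0.0411, equivalent.

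One patient in each direction, moved from discordant to concordant, changes the conclusion. This does not size the label effect, but it shows that a small effect would matter.

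**The case against.** The strongest case against has four parts.

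*The effect may be small or may cancel.* The tests are standardized, several have alternate forms, norm conversion is automated, and a fidelity checklist covers administration and scoring in a random 20% of participants. An equal label effect drops out of Aim 1. All of this stands, and it is why no size is claimed. It does not close the gap: administration and raw scoring remain with the psychometrist, most participants fall outside the fidelity sample, video sessions are not recorded and so cannot be rescored blind, and cancellation does not protect Aim 2.

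*Withholding the label leaves the larger route open.* A reader might infer that restricting REDCap access would remove most of the bias, and might read the rates in the working as the amount removed. The documents do not support that. The psychometrist personally conducts visit 1, and user rights cannot erase that memory. No share of the bias can be assigned to the label.

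*The neuropsychologists' blind may be intact.* A reader might also infer that they can open the first rater's form or the neurology-note fields. That would be inferred from silence. The access sentence concerns confidentiality and does not say that every user sees every form. The plan assigns a different neuropsychologist to each modality and, outside clinical exceptions, holds the face-to-face results note until both conditions are complete.

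*Someone must handle the label.* This is true: the psychometrist is also the coordinator. But the neurologist's referral already establishes the diagnostic criterion, a 40/40 count needs no examiner, and the interviews sampled by typical or atypical presentation follow both visits.

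**Conclusion.** The concern holds in a limited form. The plan sends the referral label, before testing, to the psychometrist, who generates the scores at both visits. This undercuts the blind that the plan relies on for the diagnoses. The exposure is clearest for Aim 2. For Aim 1 and 1b it arises only if the label acts differently by modality or shrinks scores toward an expected profile. The likely direction is toward declaring equivalence, although a modality-specific effect could go either way.

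The size is unknown: the rates in the working rest on assumed SDs and assumed pulls. That there is one psychometrist is a fair reading of the singular wording, not a stated number. The change is worth making because it is cheap and because analysis cannot remove the bias afterwards.

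**What to change.** 1. Amend Recruitment and Screening and Informed Consent and Assent so that the typical/atypical field goes to a restricted REDCap form, hidden from the psychometrist and both neuropsychologists until both visits are scored and rated.
2. Send the psychometrist only contact details, confirmation of eligibility and the capacity judgment. Confirmation of eligibility can replace the neurologist's severity rating, which bears on an Aim 2 outcome.
3. Have an existing team member with no testing or rating role, or an automated REDCap count, track the 40/40 enrolment. Release the label after both visits for interview sampling.
4. To make the plan's existing intent explicit, keep neurology-note diagnostic fields and visit-1 scores and ratings from the visit-2 neuropsychologist until visit-2 ratings are submitted. Leave the plan's exceptions for clinically urgent information as they are.
5. State in Section E that the same examiner's recall of visit 1, and possible disclosure by patients or care partners, remain as limitations.

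The cost is a change to REDCap user rights and a few protocol sentences. Handling the label moves to someone other than the psychometrist, and abstraction of the neurology notes waits until both visits are rated unless those fields sit in the restricted form. No extra visits or second examiner are needed; whether a suitable team member is available is for the sponsor to confirm.

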IV. Research Methods

A. Description of Population to be Enrolled:

Clinical Trial Participants (Patients):

We will recruit 80 patients from the **UCH Memory Disorders Clinic** (considering possible screen fails, up to 150 may ultimately be recruited). To understand the feasibility and preliminary validity of TeleNP, we will enroll 1) 40 adults with suspected **typical** AD (i.e., memory-predominant) and 2) 40 adults wherein AD is on the neurologist's diagnostic differential, but the presentation is **atypical** (i.e., complex/non-memory predominant presentations). The typical and atypical AD groups will range in severity from MCI to mild dementia (based on referring neurologist's determination); this is consistent with current conceptualizations of AD, in which clinical syndrome (AD) is distinct from severity of presentation (MCI; dementia).^{1, 2}

All participants with suspected AD will be referred by neurologists. Our specific inclusion/exclusion criteria will be:

Inclusion criteria:

Eligible participants will be adults \geq 60 years and <90 years who are undergoing evaluation for possible AD and whose severity ranges from MCI to mild dementia. Of note, we are excluding individuals aged 90 and over, as recent studies suggest that individuals in the oldest-old category differ from other individuals with MCI or dementia in terms of risk factors for AD and prevalence of non-AD pathologies.²¹⁻²³ In addition, limited age-referenced normative data for neuropsychological tests are available for individuals 90 and over, which impacts our ability to address Aims 1 and 2.

Eligible participants must carry a diagnosis of either suspected typical AD or atypical AD, based on the referring neurologist's diagnosis.

- Typical AD: Defined as a memory-predominant presentation of AD.
- Atypical/Complex AD: Defined as a complex (i.e., AD is under consideration, but other diagnoses may be included in neurologist's differential diagnosis) and/or non-memory predominant phenotype of AD.

Both patient groups will be based solely on the neurologist's clinical diagnosis after the initial Neurology visit, and in the absence of formal neuropsychological test results, to minimize circularity.

Exclusion criteria:

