F. Statistical Analysis Plan:

For **Aim 1**, we will adopt an equivalence testing framework. The null hypothesis is that there is an average difference of at least .5 SD units in the difference in the z-scores, where .5 SD defines a potentially clinically meaningful difference. The alternative hypothesis is that the mean of the

difference in the z-scores is zero. This is the reverse of standard statistical testing. We elected a .5 SD margin as an initial threshold for a clinically meaningful difference; the reason for this decision is that once an individual reaches a level deemed to be clinically significant impairment (e.g., mild impairment = -1.5 SD; moderate impairment =-2.0 SD), a change in .5 SD equates to a categorical difference in their overall severity rating. To conduct our equivalence test, we will compute the difference in the z-score between the FF and TeleNP conditions and compute the mean difference and a 90% confidence interval based on a t-test. This results in an equivalence test with an alpha=0.05. If the entirety of bounds of the 90% confidence interval are between (-.5SD, .5SD), then the two assessments will be considered equivalent. We will repeat this computation stratified by referring diagnosis (typical vs. atypical), and also by sex or race/ethnicity (white vs. non-White).

For **Aim 2**, we will compute a 3x3 table with the rows as TeleNP diagnosis and the columns as FF diagnosis to summarize the results. To assess the equivalence of TeleNP and FF for each condition we will create 3, 2x2 tables. For example, when assessing for differences in typical AD we will collapse over atypical AD and Not AD. Following prior work³⁵, we will compute the difference proportion of typical AD for the TeleNP and FF setting and construct a 90% confidence interval. A difference of proportions greater than 5% will be considered a clinically meaningful difference. If the 90% confidence interval is between (-5%,5%), then the two modalities will be considered equivalent. We will repeat this process for the two other neuropsychologist-determined categories (atypical AD, Not AD). We will conduct the same analyses, stratified by severity. We will assess whether the neuropsychologists' diagnosis is equivalent to the Flexible Assessment by repeating the above analysis using the Flexible vs FF diagnosis (i.e., diagnosis reported prior to initiating Flexible Assessment).

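### The Aim 2 TeleNP–FF interval does not use the randomised neuropsychologist assignment, so any systematic gap between the two neuropsychologists costs precision and blurs attribution to modality

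*Combined protocol and SAP*

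**What the plan says.** Section IV.B (Randomization) gives the reason for two raters: "Our goal of using two neuropsychologists is to minimize bias", because "use of the same neuropsychologist for the same patient across both modalities would likely influence their interview approach and diagnostic adjudication". It adds that "assignment of supervising neuropsychologist will be randomized and counterbalanced across testing conditions". I read this as two assignment groups: neuropsychologist A on TeleNP with B on FF, and the reverse.

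Section IV.F sets the Aim 2 rule for each of the three diagnosis categories. The diagnoses are collapsed to a 2x2 table, and then "we will compute the difference proportion of typical AD for the TeleNP and FF setting and construct a 90% confidence interval". The decision follows: "If the 90% confidence interval is between (-5%,5%), then the two modalities will be considered equivalent". No rater term or stratification by assignment is mentioned. The same analyses are to be repeated by severity.

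Section IV.E (Diagnosis) accepts that neuropsychologist-specific effects may occur, with a leaning towards the complex category as its example, and responds: "We will assess in exploratory analyses whether there were provider-specific effects on outcomes". No method is given, and the result does not feed into the interval.

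**The concern.** The design controls for rater, but the decision interval does not use that control. A rater habit pushes the TeleNP-minus-FF difference up in one assignment group and down in the other. Pooling the groups treats this known, randomised spread as random error. If the groups are unequal among the analysed pairs, part of the habit also appears as a modality effect. Section IV.A–B allows withdrawal at any time, section IV.C foresees TeleNP sessions ended by technical problems, and no blocking within severity strata is described, so unequal groups are plausible.

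At stake is whether the Aim 2 estimate and interval, which are meant to inform a later definitive trial, describe the modality alone or the modality plus a difference between two individuals.

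**Working it through.** **The plan's own figures.** The plan gives no power, expected discordance or expected width for Aim 2. The only related figure is alpha = 0.05, stated for Aim 1. It follows from a 90% interval, since (1 − 0.90)/2 = 0.05, and the same interval rule carries over to Aim 2.

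**Inputs from the documents.** 80 patients, each seen in both modalities (IV.A, IV.B); two neuropsychologists; 90% interval; margin ±5 points (IV.F).

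**Assumptions, not in the documents.** All 80 pairs are complete; the split is 40/40 unless stated; there is no modality effect; the mean category rate is 40%; the two visits have latent (probit) correlation 0.9; the interval is a paired Wald interval. The rater gap β is the difference between the two raters' probabilities of giving the category, taken as 0, 10 or 20 points.

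**Model.** Let d be the paired difference (+1, 0 or −1), τ the modality effect and π the proportion of discordant pairs.
- The mean of d is τ + β in one assignment group and τ − β in the other.
- The average of the two group means is τ. Half their difference is β.
- With τ = 0, the pooled half-width is 1.645·√(π/80).
- Stratified by assignment at 40/40, it is 1.645·√((π − β²)/80).
- π = pA + pB − 2·P(both positive), with the last term from the bivariate normal.

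**Width under balance.**

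| Gap | pA, pB | P(both) | π | Pooled | Stratified | Ratio |
|---|---|---|---|---|---|---|
| 10 points | 0.45, 0.35 | 0.3196 | 0.1609 | 7.38 | 7.14 | 1.03 |
| 20 points | 0.50, 0.30 | 0.2896 | 0.2208 | 8.64 | 7.82 | 1.10 |

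Half-widths are in percentage points. With β = 0 the two formulas are identical. Simulations of the same model gave 7.3 against 7.0 to 7.1 points at the 10-point gap, and 8.6 against 7.7 to 7.8 at the 20-point gap. At the 20-point gap, coverage was about 93% pooled and 89 to 90% stratified.

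**Dependence on π and β.** At π = 10%, a 5-point gap narrows the half-width from 5.82 to 5.74 and a 10-point gap to 5.52. At π = 30%, a 10-point gap takes it from 10.07 to 9.90. The largest gains need all discordance to be systematic: at β = π = 20%, 8.22 becomes 7.36.

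**Unequal groups.** The pooled mean is τ + β·(n1 − n2)/n. At a 20-point gap and 44/36 the shift is 0.20 × 8/80 = 2.0 points, which is 40% of the margin. The simple average of the two group differences removes it.

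**Why the two effects do not add.** Under simple randomisation the shift varies from trial to trial with variance β²/n. Adding it to the within-group variance gives (π − β²)/n + β²/n = π/n, exactly the pooled variance. The pooled interval then has nominal coverage (simulated: 90%).

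**Effect on the verdict.** A half-width of 5 points or less needs π ≤ 80 × (0.05/1.645)² = 0.074, fewer than 6 discordant pairs in 80. Enumerating 40/40 tables, the verdict changes only with exactly 6 discordant pairs split 3 and 3 by direction, and then only for some distributions across the groups (5.04 falls to between 4.84 and 4.95). With no modality effect, the simulated chance of declaring equivalence at a 10-point gap and correlation 0.97 was about 2% pooled against 4 to 5% stratified. At a 20-point gap and correlation 0.9 it was practically zero for both.

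**The case against.** The strongest reply has four parts.

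- **Rater effects are foreseen.** Section IV.E names them and commits to an exploratory look. This stands. A reader might infer that the plan overlooks rater differences altogether, and it does not. What is missing is their use in the decision interval.
- **The verdict hardly depends on it.** This stands. A reader might infer that rater differences would drive a non-equivalence result. The arithmetic does not support that: in the settings above the half-width exceeds 5 points with or without stratification. The obstacle is 80 patients against a 5-point margin.
- **Counterbalancing already protects the estimate, and the error is in the safe direction.** This largely stands. With balanced groups the pooled estimate is unbiased and the interval conservative, so false equivalence is not the risk. But counterbalancing governs allocation, not which pairs remain in the analysis. The 44/36 split is illustrative, because the documents give no dropout figure.
- **Only a systematic gap can be removed.** This stands. Case-by-case disagreement between raters remains in every pair and cannot be separated from modality, because no patient has two raters within one modality.

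The interval method is also not visible: section IV.F refers to prior work that the available text does not identify. The widths above therefore rest on an assumed paired Wald interval.

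**Conclusion.** The point holds as an inexpensive improvement in precision and attribution. It does not show that the Aim 2 conclusion is wrong. Its size depends wholly on an assumed systematic rater gap. Under the stated assumptions and balanced assignment, the pooled interval is about 3 to 4% too wide at 10 points, about 10% too wide at 20 points and unaffected at zero. With unequal analysed groups the estimate moves by the gap times the relative imbalance.

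A reader might add the excess width to the chance shift as two separate harms. They should not be added: the first arises when balance is fixed, and under simple randomisation the pooled variance already contains the second.

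The point does not reach the Flexible versus FF comparison, where the same neuropsychologist rates before and after the extra tests.

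**What to change.** In section IV.F, for each TeleNP–FF category under Aim 2:

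1. Compute the TeleNP-minus-FF difference within each of the two neuropsychologist-assignment groups.
2. Take the simple average of the two as the modality effect, with standard error ½·√(SE₁² + SE₂²), and base the 90% interval on it. Name the paired-proportion method used.
3. Report half the between-group difference as the rater effect, beside the modality effect.
4. State that case-by-case rater disagreement remains mixed with modality.

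Optionally, have REDCap allocate the four combinations of modality order and neuropsychologist assignment in blocks within the typical and atypical referral groups. This helps keep the groups even. The stratified estimate handles whatever imbalance is left, including in the severity strata.

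The cost is a few sentences of SAP text, one stored variable that the randomisation already creates, one degree of freedom and, if blocking is adopted, a revised allocation table. No extra patients or visits are needed.
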